Power and Sample Size Estimation. We will enroll 30 patients per group. Based on our experience with randomized trials in PAD, we anticipate that 27 participants in each group will complete 6-month follow-up and provide outcomes for the statistical analysis (44,74). For Primary Aim 1, we will use a two-sample t-test to compare the 6-month decline in six-minute walk distance between NR alone and placebo. Twenty-seven participants per group provides 80% power for detecting a difference of 0.69 standard deviation (SD) of the decline at the one-sided significance level of 0.1. Based on our GOALS Trial results (74), a 0.58 SD represents a difference of 30 meters in six-minute walk distance. Similarly, for Primary Aim 2, we will have 80% power for detecting a difference of 30 meters between NR combined with resveratrol vs. placebo. For Secondary Aim #1 and Secondary Aim #2, we will have 80% statistical power for detecting a difference of 30 meters between the NR alone vs. placebo group (Secondary Aim #1) and between the NR combined with resveratrol group vs. the placebo group (Secondary Aim #2) at 3-month follow-up. In our Secondary Aim #3, we will have 80% statistical power for detecting a difference of 30 meters between the NR combined with resveratrol group and the NR alone group at 3-month and at 6-month follow-up. Most prior studies have defined clinically meaningful changes in the six-minute walk as 20-50 meters (77-80). Thus, the study has sufficient statistical power for detecting a clinically meaningful difference under the same assumptions. The NICE Trial is a proof of principle study intended to collect evidence for a large randomized trial. For Secondary Aim #4, we will compare changes in maximal treadmill walking distance, the WIQ distance score and physical activity between NR alone vs. placebo. The study provides 80% power for detecting a difference of 0.58 SD. Similarly, in Secondary Aim #5, we will compare changes in maximal treadmill walking distance, the WIQ distance score and physical activity between NR + resveratrol and placebo. In our GOALS trial, 0.69 SD of 6-month decline in WIQ represented a difference of 14 points for the WIQ distance score (74). The difference in reported cut-off values in WIQ scores between high and low PAD performers is 76 minus 43, or 33 points (83). Therefore, the study should have sufficient statistical power for detecting clinically important differences in the WIQ distance score. For Secondary Aim 6, we will compare 6-month changes in maximal treadmill walking distance, the WIQ distance score, and physical activity between people randomized to NR combined with resveratrol, compared to NR alone. For Secondary Aim 7, we will compare 3-month and 6-month changes in six-minute walk distance between all people randomized to an NR group (i.e. those randomized to NR combined with resveratrol and those randomized to NR alone) and those randomized to placebo. For Secondary Aim 8, we will compare 6-month changes in maximal treadmill walking time, the WIQ distance score, and physical activity between all people randomized to an NR group (i.e. those randomized to NR combined with resveratrol and those randomized to NR alone) and those randomized to placebo. In Secondary Aims #7 and #8, we have 80% power for detecting a difference of 0.50 SD. The proposed mixed effects regression analysis has a higher power than the two-sample t-test and thus can detect even smaller differences.

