
Statistical Analyses. Analyses will be performed using the intention to treat principle. Prior to the analyses, the distributions of the variables (changes) will be examined. For our Primary Aim #1, we will use a mixed effects repeated measurements (MMRM) regression to compare changes in six-minute walk performance at 6-month follow-up between the NR alone vs. placebo groups, adjusting for age, sex, race, and baseline six-minute walk distance. Age, sex,

and race will be adjusted for because of their association with change in six-minute walk distance (see below). Similar analyses will be performed for Secondary Aims #1, #2, #3, and #7. For our Primary Aim #2, we will use a one-tailed t-test based on MMRM to compare changes in six-minute walk between NR combined with resveratrol vs. placebo. We will perform MMRM regression analysis with the change in six-minute walk distance at month 3 and month 6 as the correlated response variable with an unstructured covariance matrix to evaluate differences in change in six-minute walk distance between the two groups in each comparison, adjusting for potential baseline confounders specified as following: baseline six-minute walk performance, age, sex, and race. The mixed effect regression would include patients missing the 6 month follow-up visit, assuming missing at random. If either primary aim is positive, the clinical trial will be considered positive. A one-sided P value at $P<0.10$ will be considered statistically significant. We are selecting this P value because of the preliminary (pilot) nature of this work. For Secondary Aims #4, #5, #6, #8 and Exploratory Aims, we will use the analysis of covariance to compare the 6-month change of each outcome, separately. In each specific comparison, the baseline value for the outcome of interest (i.e. WIQ score, treadmill, physical activity) will be adjusted for (rather than the six-minute walk) in addition to age, sex and race. For the Secondary Aims #7 and #8, the NR + placebo groups will be combined with NR + resveratrol into one group and compared to the placebo group and the MMRM regression or analysis of covariance will additionally adjust for the resveratrol usage.

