For all of the analyses, The MMRM regression includes treatment indicator, visit time (month 3 and month 6 as categorical factors), the interactions between treatment and visit time, baseline six minute walking distance (for all aims in which six-minute walk is the outcome), age, sex and race. For comparisons of other endpoints not measured longitudinally, the conventional analysis of covariance will be used adjusting for the baseline level of the corresponding outcome, age, sex, and race. We will adjust for baseline six-minute walk, age, sex, and race, because these variables have been correlated significantly with either change in six-minute walk or with six-minute walk at follow-up in our prior studies. For example, in the combined data from the control groups of our GOALS, LITE, PROPEL, and TELEX randomized clinical trials of exercise interventions for people with PAD, six-minute walk at baseline was correlated with six minute walk distance at six-month follow-up (Pearson correlation coefficient= 0.812, $P<0.001$). In addition, participants who were Black had significantly poorer six-minute walk, compared to those who were not Black, at six-month follow-up (320.9 meters (SD: 104.5) vs. 359.8 meters (102.5), $P=0.0035$). Women had significantly poorer six-minute walk, compared to men, at six-month follow-up (309.6 (SD: 103.2) vs. 358.7 (SD: 102.1), $P<0.001$). In our observational WALCS cohort of men and women with PAD, older age was associated significantly with greater decline in six-minute walk distance at one-year follow-up (correlation= -0.236, $P<0.001$).

In a sensitivity analysis, we will repeat all comparisons additionally adjusting for baseline covariates that show major imbalances between relevant treatment groups, where the major imbalance is defined as Cohen's effect size being greater than 0.5. The MMRM analysis for comparing the change in six-minute walking distance will be based on all participants who have their six minute walking distance measured at least once during follow-up (i.e. at least at month 3 or month 6).

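### Secondary Aims #7 and #8: adjusting the combined-NR comparison for resveratrol use turns it back into NR alone versus placebo, so the combined-group effect is not estimated

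*Combined protocol and SAP*

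**What the plan says.** Under Study Endpoints, Secondary Aim #7 merges the NR alone and NR + resveratrol groups and asks whether the merged group does better than placebo on six-minute walk at 3 and 6 months. Secondary Aim #8 asks the same for treadmill time, WIQ distance score, physical activity and the calf muscle measures.

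Under Statistical Analyses, the MMRM is used "to evaluate differences in change in six-minute walk distance between the two groups in each comparison". Its terms begin as follows: "The MMRM regression includes treatment indicator, visit time (month 3 and month 6 as categorical factors", then treatment by visit, baseline six-minute walk, age, sex and race. Outcomes without repeated measures use ANCOVA. For Aims #7 and #8 one term is added: "the MMRM regression or analysis of covariance will additionally adjust for the resveratrol usage". The significance rule is: "A one-sided P value at $P<0.10$ will be considered statistically significant".

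Under Power and Sample Size Estimation: "We will enroll 30 patients per group", and "we anticipate that 27 participants in each group will complete 6-month follow-up". That section states 80% power for Aims #7 and #8 at a difference of 0.50 SD.

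On who takes resveratrol, the Intervention and placebo paragraph gives it to the NR + resveratrol arm only. Exclusion criterion 15 bars current resveratrol users and anyone who took it in the past six months.

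**The concern.** The design has no resveratrol-only arm. Within the trial, resveratrol use is therefore the same variable as membership of the NR + resveratrol arm. A model with a combined-NR indicator and a resveratrol indicator has one parameter for each arm difference. It is a three-arm model in another parameterization, and its NR coefficient no longer describes the merged group.

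Three things are at stake.

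- **The question.** Aims #7 and #8 would report roughly what Primary Aim #1 and Secondary Aim #4 already report, under a label that says both NR arms combined.
- **The power.** Merging the arms is meant to give 54 versus 27. The added term gives up most or all of that gain.
- **The reading.** Agreement between Aim #7 and Primary Aim #1 could be taken as support from a larger comparison when it is close to the same estimate twice.

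**Working it through.** **Inputs.** From the plan: 27 completers per arm, one-sided alpha 0.10, 80% power, and 0.50 SD for Aims #7 and #8. The statement that "a 0.58 SD represents a difference of 30 meters in six-minute walk distance" implies an SD of 30/0.58 = 51.7 m. Normal quantiles: 1.2816 (alpha) and 0.8416 (power), sum 2.1232.

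**1. The plan's own figure.** SE in SD units for 54 versus 27 is √(1/54 + 1/27) = √0.05556 = 0.2357. Detectable difference: 2.1232 × 0.2357 = 0.500 SD (0.503 with the t distribution). The stated 0.50 SD reproduces, but only for merged NR against placebo with no resveratrol term.

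**2. What the coefficient estimates.** Write the adjusted mean changes, at one visit, as:
- placebo: μ
- NR alone: μ + δ
- NR + resveratrol: μ + δ + ρ

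Here δ belongs to the combined-NR indicator and ρ to the resveratrol indicator. Subtracting placebo from NR alone leaves δ, so δ is NR alone minus placebo. The effect of the merged group with equal arms is [δ + (δ + ρ)]/2 = δ + ρ/2. The reported coefficient omits ρ/2.

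To give ρ/2 a scale, assume resveratrol 125 mg added to NR the 16.9 m that the protocol's Background reports for it against placebo. Then ρ/2 = 16.9/2 = 8.45 m. The plan does not say that the effects add; this is an illustration only.

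**3. Power with the term (ANCOVA, or MMRM with resveratrol crossed with visit).** The comparison is effectively 27 versus 27.
- SE = √(2/27) = 0.2722, against 0.2357 without the term: a ratio of 1.155, or 1.33 in variance.
- Detectable difference = 2.1232 × 0.2722 = 0.578 SD, or 29.9 m against 25.9 m (0.500 × 51.7).
- Power at 0.50 SD = Φ(0.50/0.2722 − 1.2816) = Φ(0.556) = 71%.

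**4. MMRM with resveratrol as a single term, not crossed with visit.** With equal arms, complete data and equal variances at the two visits, the month-6 NR coefficient is the merged-group difference minus half the visit-averaged ρ. Let ρ₃ and ρ₆ be the resveratrol effects at months 3 and 6. The coefficient then equals NR alone minus placebo at month 6 plus (ρ₆ − ρ₃)/4. If ρ does not change between visits, it is again NR alone versus placebo.

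Its variance is 1/18 + (1/4)(2/27)(1 + r)/2, where r is the residual correlation between visits. The plan does not give r. With r assumed to be 0.6, the variance is 0.0556 + 0.0148 = 0.0704 and the SE is 0.265. The detectable difference is 0.56 SD and power at 0.50 SD is about 73%. For r from 0.4 to 0.8, power runs from about 74% to 72%.

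**5. A separate discrepancy in the same section.** For the primary aims the plan states "80% power for detecting a difference of 0.69 standard deviation (SD) of the decline at the one-sided significance level of 0.1", then translates 0.58 SD into 30 m. At 27 per group, 0.58 SD reproduces (0.578 normal, 0.582 t). At 0.69 SD the power would be 89.5% (normal) or 89.1% (t). The figures above rest on 0.58 SD = 30 m only for conversion to metres.

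**The case against.** **The term may be deliberate.** The effect of NR with resveratrol held fixed is a legitimate quantity. That stands, but in this design it is the NR alone versus placebo effect, which is already Primary Aim #1. It is not the merged-group question that Aims #7 and #8 pose.

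**The term may mean resveratrol taken outside the study.** The wording does not rule this out. Criterion 15 removes current and recent users at entry, so a baseline variable would be nearly constant. Use during follow-up would be a post-randomization variable. Neither is described.

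**The information is still in the model.** This is correct: δ + ρ/2 can be formed afterwards as a linear combination. The plan does not say it will be.

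**A reader might infer a wider fault:** that every six-minute walk comparison discards an arm, and that one three-arm MMRM would be tighter for free. The documents do not support this.
- Aim #7 itself uses all three arms.
- For the pairwise aims, separate two-group fits are the natural reading, but nothing says the third arm is left out. The MMRM analysis set is everyone with at least one follow-up walk.
- The gain is small. The ANCOVA variance factor is 1 + p/(N − g − p − 1), with p covariates, N patients and g arms. With p = 4 (race taken as one binary term) it is 1.085 for two arms (N = 54) and 1.055 for three (N = 81). The SE ratio is √(1.055/1.085) = 0.986, and power at 0.58 SD is 77.2% against 78.3%. In 700 simulated MMRM trials (r = 0.6, 5% missing at month 3 and 10% at month 6) the SE ratio was 0.989. Power was 79.6% pairwise and 79.1% joint, within simulation error, and the joint SE was larger in 40% of trials.
- It is not free. In 20,000 simulated ANCOVAs with a different SD in the third arm, the pooled model's one-sided type I error for NR versus placebo was 0.129 at an SD ratio of 0.6 and 0.068 at 1.5. The pairwise fit stayed near 0.10. The SD ratios are assumptions.

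What a joint model does offer is contrasts that add up. In 5,000 simulated month-6 analyses, separately fitted differences failed to add by a median of 3.1 m (95th percentile 10.4 m). No decision rule in the plan depends on that.

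**Conclusion.** Wrong as written, for Secondary Aims #7 and #8 only. With the resveratrol term the NR coefficient is NR alone versus placebo: exactly in the ANCOVA and in an MMRM with resveratrol crossed with visit, and up to a quarter of the between-visit change in the resveratrol effect otherwise. The stated 80% power at 0.50 SD becomes about 71%, or about 73% in the uncrossed MMRM at r = 0.6. The detectable difference rises from 0.50 to about 0.58 SD (0.56 uncrossed).

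This assumes that resveratrol usage means assigned resveratrol, that 27 per arm complete, and that variances are equal. The power figures follow the plan's own unadjusted two-sample basis. They do not apply to the biopsy outcomes in Aim #8, because the biopsy is optional.

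The primary aims and the rule for a positive trial are unaffected. For the pairwise aims there is only an unclear specification. The choice between joint and pairwise fitting is a trade-off, and the plan should state it.

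**What to change.** 1. In Statistical Analyses, delete the resveratrol adjustment for Aims #7 and #8. Define the combined effect as the mean of the two NR arms minus placebo, from a model with a three-level treatment factor: at months 3 and 6 in the MMRM for Aim #7, and at month 6 in the ANCOVA for Aim #8. The 0.50 SD power statement can then stay.
2. If an NR effect net of resveratrol is also wanted, say that it is the NR alone versus placebo contrast and do not present it as the combined-group result.
3. For the pairwise six-minute walk aims, state whether one three-arm MMRM with contrasts or separate two-group fits will be used, and whether the unstructured covariance is common to all arms or arm-specific. A joint model is optional. Arm-specific covariance protects the type I error but gives back much of the small precision gain.

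The cost is a few sentences of SAP text and contrast statements in the code. No patients, visits or measurements are added.

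### Treadmill time: the six-month ANCOVA leaves out anyone untested at month 6, even those with a month-3 walk; imputing from that walk is a cheap improvement

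*Combined protocol and SAP*

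**What the plan says.** The Statistical Analyses section opens with a general principle: "Analyses will be performed using the intention to treat principle". It then treats two kinds of outcome differently.

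- **Six-minute walk.** Changes at months 3 and 6 enter an MMRM. Participants who miss month 6 stay in under missing at random. On the analysis set, the plan states: "The MMRM analysis for comparing the change in six-minute walking distance will be based on all participants who have" at least one follow-up walk, at month 3 or month 6.
- **Treadmill time and the other secondary and exploratory outcomes.** Here "we will use the analysis of covariance to compare the 6-month change of each outcome, separately". The same section adds: "For comparisons of other endpoints not measured longitudinally, the conventional analysis of covariance will be used". The covariates are the outcome's own baseline, age, sex and race; the outcome's baseline takes the place of the six-minute walk.

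Under Procedures Involved, the six-minute walk is the only performance test named for the three-month visit. The treadmill test is done at baseline and repeated at six months.

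On expected loss, the Power and Sample Size Estimation section says "We will enroll 30 patients per group" and "we anticipate that 27 participants in each group will complete 6-month follow-up and provide outcomes for the statistical analysis".

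The only sensitivity analysis adds baseline covariates that turn out imbalanced. No missing-data rule is given for treadmill time.

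**The concern.** The plan never calls the treadmill analysis complete-case; that is an inference. But a conventional ANCOVA of the six-month change, with no imputation rule, has no value to use for someone untested at month 6. So the trial collects a month-3 walk, uses it to handle missing data for one walking outcome, and leaves it unused for the other.

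The two results could then rest on somewhat different participants and condition on different information. If participants whose walking had worsened by month 3 were lost more from one arm, the treadmill contrast would be shifted although data to reduce the shift were in hand. The false-positive direction arises when an active arm loses its poor walkers. It matters because the results are meant to guide the design of a definitive trial.

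**Working it through.** **1. Inputs from the plan.** 30 enrolled and 27 expected to complete per arm. Expected loss is 1 − 27/30 = 10%, or 3 per arm and 9 of 90 overall. The test rule is "A one-sided P value at $P<0.10$ will be considered statistically significant". For Secondary Aim #4 the plan claims 80% power at 0.58 SD.

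**2. Reproducing the plan's figure.** Power = Φ(δ√(n/2) − z₀.₉₀) = Φ(0.58 × √13.5 − 1.282) = Φ(0.849) = 80.2%. The noncentral t gives 79.7%. The stated power therefore already assumes completers only and is not misstated.

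**3. Precision at stake.** If all 30 per arm had a month-6 treadmill value, power would be 82.9% (noncentral t), which is the ceiling. Using the month-3 walk recovers less. Let r be its partial correlation with treadmill change and k the number of month-6 non-completers per arm who have a month-3 walk. Then n_eff = 1 / [(1 − r²)/27 + r²/(27 + k)]. For r = 0.5 and k = 3, n_eff = 1/(0.75/27 + 0.25/30) = 27.7. Over r = 0.2 to 0.7 and k = 1 to 3 (assumed), n_eff is 27.0 to 28.4 and power 80.3% to 81.7%. The gain in power is small.

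**4. Bias by arithmetic.** An arm's completer mean is off by (fraction missing) × (completer mean − non-completer mean). With 10% missing in each arm, only a between-arm difference D in that gap shifts the contrast, by 0.10 × D. For D = 0.25, 0.5 and 1.0 SD (assumed), the shift is 0.025, 0.05 and 0.10 SD, which is 4%, 9% and 17% of 0.58 SD.

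**5. Bias by simulation.** Assumptions: 30 per arm; 3 lost per arm, all with a month-3 walk; no true effect; treadmill change = −0.3 × baseline + ρ × month-3 walk change + noise, with ρ = 0.3 / 0.5 / 0.7. Complete-case ANCOVA on arm and baseline, one-sided 0.10. Loss is drawn with weights exp(−c × month-3 change).

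- Random loss in both arms: bias about 0, rejection about 9–10%.
- Strong selection (c = 2) in both arms: bias 0.005 / 0.000 / 0.001 SD, rejection 10–11%.
- Weak selection (c = 0.5) in one arm: 0.015 / 0.024 / 0.041 SD.
- Moderate selection (c = 1) in one arm: about 0.03 to 0.06 SD (0.07 in some runs at ρ = 0.7).
- Strong selection (c = 2) in one arm: about 0.04 / 0.07 / 0.10 SD.

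The sign depends on which arm loses its poor walkers. Under strong selection, rejection falls to about 7.1 / 5.7 / 5.5% if that arm is placebo. If it is the active arm, false-positive rates are about 12–19% across moderate and strong selection.

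**6. The alternative.** Multiple imputation using the month-3 walk had bias under 0.01 SD and rejection near 10% under strong one-arm selection. With six predictors fitted within arm on 27 observed participants, the SD of the estimate under random loss was 0.28–0.29 for both methods. The imputation cost no meaningful precision.

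**The case against.** Several points on the other side stand.

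- **The upper end is a stress case.** With c = 2, someone 1 SD below the mean is e⁴ ≈ 55 times as likely to be lost as someone 1 SD above. The other arm must lose people at random, and all three lost per arm must have a month-3 walk. None of this is in the documents, and differential selection is harder to expect in a double-blind trial. Even then the bias is under 0.4 of a standard error (0.10/0.27 = 0.37).
- **The design limits loss.** Participants who stop the intervention are still asked back (Withdrawal of Participants), the month-6 visit can be late (Procedures Involved), and travel support can be extended (Compensation for Participation in Research Activities). These provisions may reduce missing data, but they do not say how to analyse what remains.
- **The difference between methods is partly structural.** Treadmill time has one follow-up value, so an MMRM of treadmill time alone would gain nothing. Both analyses can be read as missing-at-random analyses that condition on different information.

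A reader might infer more than the documents support:

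- *That the ANCOVA is valid only if dropout is unrelated to everything outside the model.* It is not so: loss equally related to month-3 walking in both arms left the contrast unbiased.
- *That a full 10% per arm is dropped by the ANCOVA and kept by the MMRM.* Anyone missing both visits leaves both analyses. The documents do not say how the expected 3 per arm divide, so the number is 0 to 3.
- *That treadmill time is a special case.* The other ANCOVA outcomes share the gap.

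**Conclusion.** This is a cheap improvement to a secondary analysis, not the correction of an error that threatens the trial. The treadmill ANCOVA as written cannot use month-6 non-completers, and it leaves unused a month-3 walk that some of them will have. The primary aims and the stated power are unaffected.

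Bias arises only if loss related to month-3 walking differs between arms. The 0.03 to 0.10 SD range rests on assumed correlations of 0.3 to 0.7, on moderate to strong selection in one arm only, and on all 3 lost per arm having a month-3 walk. With fewer such participants, the imputation has less to work with. If loss is random or equally selective, the two methods agree. The case for the change is that it costs almost nothing when it is not needed, and that naming the rule in advance removes a choice that would otherwise be made after the data are seen.

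**What to change.** In Statistical Analyses, add two or three sentences for maximal treadmill walking time:

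1. Run the specified ANCOVA after multiple imputation, by randomized arm, of missing six-month treadmill values. The predictors are baseline treadmill time, age, sex, race, and baseline and month-3 six-minute walk. A joint model of treadmill change with the walk changes is an equivalent choice.
2. Include every randomized participant who has either a six-month treadmill value or a follow-up walk. Restricting the set to those with a follow-up walk would wrongly drop anyone with an observed treadmill test but no walk.
3. State the missing-at-random assumption and report the complete-case ANCOVA as a sensitivity analysis.

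The same approach can serve the other ANCOVA outcomes.

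The cost is a little more programming; no new data, visits or participants are needed. The result relies on missing at random, which the primary MMRM already assumes. The change does not settle how deaths are handled, and it does not help participants with no follow-up data at all.
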